8.7.1. Events of interest in the study during follow-up

- Death from any cause
- Acute ischemic syndrome: Diagnosis of acute myocardial infarction or unstable angina.
- New diagnosis of heart failure with preserved or impaired ventricular function.
- Vascular revascularization: performance of myocardial revascularization surgery, coronary angioplasty or peripheral vascular angioplasty.
- Cerebrovascular event: Diagnosis of cerebrovascular accident ("stroke") or transient ischemic attack.
- Cancer: new diagnosis of any type of cancer

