1. To classify transcriptomes according to the presence and extent of coronary calcification by noncontrast cardiac CT.
2. Train artificial intelligence algorithms with information from the transcriptome to recognize the presence and extent of calcification in coronary arteries.

-
3. To determine the degree of diagnostic accuracy of the method to detect the presence and extent of coronary calcification non-invasively.

Secondary objectives

1. To determine the degree of diagnostic accuracy of the method to detect the presence and extent of:
 - Aortic
 - calcification Aortic valve calcification
 - Hepatic steatosis
 - Volume of epicardial fat
 - Volume of high-density epicardial fat (upper quartile)
 - Enlargement of cardiac cavities To
2. To explore differences in transcriptomics of peripheral blood between patients who did and did not develop a CV event during follow-up.
3. To explore different electrocardiographic patterns according to the results of cardiac CT and peripheral blood transcriptomics.
4. Generate a polygenic risk score (PRS) from the transcriptome and/or exome sequencing and associate it with the transcriptome and coronary calcification.

7. Methods

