7.1. Study Design

This trial will be a prospective observational study. A convenience sample will be carried out to include 800 patients who attend the ENERI Medical Institute, La Sagrada Familia Clinic, to undergo a cardiac CT without contrast (coronary calcium score), either for a medical indication or volunteers to an assessment of cardiovascular risk. The study will have a baseline stage in which a clinical evaluation will be performed, blood samples will be drawn for transcriptome analysis and laboratory analysis. Then, a DNA sample

obtained by swabbing the buccal mucosa will be taken. Subsequently, a non-contrast gated cardiac CT will be performed to assess the presence and extent of coronary calcification and other results of interest. At the end of patient enrollment, biological samples will be sequenced for in silico evaluation of the results. Finally, a 5-year clinical (telephone) follow-up will be carried out to collect data on the incidence of fatal and non-fatal cardiovascular events.

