7.2. Study Population

7.3. Inclusion Criteria

- Men and women between 30 and 75 years attending the institution for a non-contrast cardiac CT scan (coronary calcium score) either by medical indication or voluntary for cardiovascular risk assessment.
- Signature of informed consent form

7.4. Exclusion criteria.

- Previously known chronic renal or hepatic insufficiency.
- Active chronic lung disease, defined as: exacerbated asthma, exacerbated COPD, or pulmonary fibrosis.
- Active and/or previous cardiovascular disease, defined as: previous acute myocardial infarction, stable or unstable angina, cerebrovascular accident, history of vascular interventions (coronary or other territory), heart failure, severe cardiomyopathies or valvulopathies.
- Uncontrolled hyper or hypothyroidism.
- Suprarrenal insufficiency.
- Previous surgeries in the last 3 months.

-
- Severe trauma in the last 6 months, defined as one that involved bone fractures and/or surgical interventions.
 - Known active cancer disease or under treatment (acute or preventive), or history of cancer disease without criteria for cure.
 - Known autoimmune disease active or in treatment.
 - Ongoing pregnancy, postpartum period of less than 12 months or breastfeeding.
 - Other serious illness with an estimated life expectancy of less than 12 months (according to the investigators).
 - Temperature greater than 37.5°C recorded by a thermometer or any acute infection caused by viruses or bacteria confirmed by a health professional in the previous 30 days.
 - Pathologies under immunosuppressive treatment

8. Procedures

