8.7. Patient follow-up

Patients included in the study will be contacted annually by phone call to collect the following data:

- Vital status.
- Cardiovascular events: New episodes of hospitalization due to acute ischemic syndrome, cerebrovascular event, heart failure or revascularization.
- New diagnoses of relevant chronic diseases.

If they cannot be contacted, the "alternative means of contact" provided by the patient will be used, in order to know their vital status or obtain a new contact number.

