8.7.2. Verification and adjudication of events during follow-up

When an event of interest is reported during study follow-up, the "phase of verification" that consists of obtaining data on: type of event, date, place where it was treated and its corresponding source document (death certificate, epicrisis, complementary study, evolution of clinical history, etc.) where the diagnosis of the event appears with a doctor's signature. The study event adjudication committee will be made up of three medical investigators ([name]). Each of the members will analyze the documentation sent for the case separately and will adjudicate the event. If there is no agreement, it will be awarded by majority.

9. Guarantee and quality control of the data

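### Revascularisation counts as a follow-up event whatever its indication, so procedures prompted by the baseline calcium CT can enter the event group of exploratory secondary objective 2.

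*Combined protocol and SAP*

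**What the plan says.** The annual telephone call (section 8.7) collects "Cardiovascular events: New episodes of hospitalization due to acute ischemic syndrome, cerebrovascular event, heart failure or revascularization". Section 8.7.1 then lists the events of interest, among them "Vascular revascularization: performance of myocardial revascularization surgery, coronary angioplasty or peripheral vascular angioplasty". Neither section mentions indication, urgency or a window after the scan. They also differ from each other: 8.7 is worded around admission to hospital, 8.7.1 around the procedure being done.

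The analysis that uses these events is secondary objective 2 in section 6: "To explore differences in transcriptomics of peripheral blood between patients who did and did not develop a CV event during follow-up". The term CV event is not defined further, so on a plain reading of 8.7 and 8.7.1 revascularisation is included.

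Participants come for the calcium score "either for a medical indication or volunteers to an assessment of cardiovascular risk" (section 7.1). Section 7.4 excludes people with "previous acute myocardial infarction, stable or unstable angina, cerebrovascular accident, history of vascular interventions (coronary or other territory" and other known cardiovascular disease. Verification under section 8.7.2 obtains "type of event, date, place where it was treated and its corresponding source document". Three medical investigators then review each case: "Each of the members will analyze the documentation sent for the case separately and will adjudicate the event". No rule on indication is given to them, and no blinding is stated. The analysis plan (section 9.4) contains no analysis of objective 2.

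**The concern.** Everyone enters without known cardiovascular disease, and the baseline CT may be what initially leads to further work-up. Take two participants with the same very high score and no symptoms. One is investigated because of the score and has an elective angioplasty; the other is not. Under 8.7.1 the first is an event patient and the second is not, although their spontaneous course is the same.

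The event label is then partly produced by coronary calcification, the same characteristic that the study's algorithm is trained to recognise (specific primary objective 2). A transcriptome difference between event and no-event patients could partly reflect calcification acted on by clinicians, and the plan records nothing that would separate this from prognosis. Events are likely to be few among 800 people without known disease, so a small number of such procedures could matter.

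**Working it through.** **Plan's own figure.** There is none to reproduce. The documents give no event count, event rate or power for objective 2. The 800 in section 9.3 rests on algorithm training and comes with no alpha, power, effect size or event rate.

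**Inputs.** N = 800 is from the protocol; the rest are assumptions.
- Severe coronary calcification: 64 of 800 (8%).
- Spontaneous CV events over 5 years: S = 40, unrelated to calcification, so 40 × 0.08 = 3.2 occur in severe patients.
- CT-prompted procedures: c = 3 to 13, all in severe patients (5% to 20% of the 64).

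**Step 1: perfect marker of severe calcification.**
- Events = 40 + c, of which severe = 3.2 + c.
- Non-events = 760 − c, of which severe = 60.8 − c.
- The non-severe counts are 36.8 and 699.2, whatever c is.
- Odds ratio = [(3.2 + c) / 36.8] ÷ [(60.8 − c) / 699.2].
- For c = 3: (6.2 / 36.8) ÷ (57.8 / 699.2) = 2.04.
- For c = 13: (16.2 / 36.8) ÷ (47.8 / 699.2) = 6.44.

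**Step 2: imperfect marker.** With sensitivity = specificity = s, the marker-positive share in a group with severe share p is p·s + (1 − p)(1 − s).
- For c = 13, the severe share is 16.2/53 = 0.306 in events and 47.8/747 = 0.064 in non-events.
- At s = 0.80 the marker-positive shares are 0.383 and 0.238, giving an odds ratio of 1.99.

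| c | CT-prompted share of events | OR, perfect marker | OR, s = 80% | OR, s = 70% |
|---|---|---|---|---|
| 0 | 0% | 1.00 | 1.00 | 1.00 |
| 3 | 7% | 2.04 | 1.23 | 1.13 |
| 6 | 13% | 3.19 | 1.46 | 1.25 |
| 10 | 20% | 4.94 | 1.76 | 1.40 |
| 13 | 25% | 6.44 | 1.99 | 1.51 |

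**Step 3: vary the spontaneous events.** With S between 20 and 60 and c between 3 and 13, the odds ratio runs from 1.71 to 11.53 for a perfect marker, 1.16 to 2.78 at 80%, and 1.09 to 1.89 at 70%.

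**Step 4: a second set-up.** Let a share q of participants have high calcium, let the clinical event risk h be independent of it, and let a fraction r of high-calcium patients without a clinical event have a CT-prompted procedure.
- Risk ratio for high against lower calcium = [h + (1 − h)r] / h.
- With q = 15%, h = 4%, r = 6%: (0.04 + 0.96 × 0.06) / 0.04 = 2.44. There are 800 × 0.04 = 32 clinical events and 120 × 0.96 × 0.06 = 6.9 CT-prompted procedures, so 18% of 38.9 events are CT-prompted.
- Over q 10–25%, h 2–6% and r 3–10%, the risk ratio runs from 1.47 to 5.90 and the CT-prompted share from 4% to 55%.
- With r = 0 the risk ratio is 1.00 throughout, so in this set-up the whole effect comes from counting those procedures.

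**The case against.** Four objections carry weight.

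1. **The perfect-marker figures are a ceiling.** Objective 2 compares transcriptomes. Whether blood can read calcification is the study's primary question, and the preliminary calcium data in section 5.2 are 38 samples with a moderate result. The 80% and 70% columns show how quickly the distortion shrinks. This stands, and it limits the size.

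2. **A true odds ratio of 1.0 is not the documents' own premise.** The introduction describes coronary calcification as having established prognostic value. A calcification-related transcriptome would then differ between the groups without any CT-prompted procedure. This also stands: what matters is the inflation added to any real association, and the calculations above do not estimate that.

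3. **No rate of CT-prompted procedures is given.** The documents do not say that scans will lead to procedures or describe how results are disclosed. They only fail to exclude or record it. This stands, so the problem is a possibility that the plan leaves open, of unknown size.

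4. **The objective is exploratory and the information is partly recoverable.** Objective 2 has no test or threshold, and 8.7.2 already gathers dates and source documents. This lowers the priority. It also makes the remedy cheap, and indication is easier to record at adjudication than to reconstruct after five years.

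A reader might infer that objective 2 will rediscover calcification in place of clinical events. The documents do not support that. Infarction, unstable angina, stroke, transient ischaemic attack and heart failure also count, and some link with calcification may be real. Nor does 8.7.1 cover every peripheral revascularisation; it names peripheral angioplasty only.

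**Conclusion.** The point holds as a gap in the event definition. As written, the rule lets the index scan contribute to the event group of objective 2, and no planned record or analysis would show how much. The direction is towards inflating calcium-related transcriptome differences.

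The size is unknown. The illustrative odds ratios of 2.0 to 6.4 (perfect marker) and about 1.2 to 2.0 (80% sensitivity and specificity) rest wholly on the assumed 64 severe patients, 40 unrelated spontaneous events and 3 to 13 CT-prompted procedures, and should not be read as expected values. Any such effect would come on top of a real association between calcification and events. Because the primary diagnostic accuracy analysis uses the baseline CT and not follow-up events, it is untouched. This is a cheap improvement to an exploratory objective, not a flaw in the main result.

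**What to change.** - **Sections 8.7.1 and 8.7.2:** have the existing committee, blind to the transcriptome result, record for each revascularisation whether it was urgent or elective, whether the baseline CT prompted it, and the time since that CT. The source documents already being obtained can be used. Blinding to the CT is not practical for the second item.
- **Objective 2 and section 9.4:** state which 8.7.1 events make up a CV event, including how death is handled.
- **Sections 8.7 and 8.7.1:** reconcile admission for revascularisation with performance of the procedure.
- **Reporting:** give the comparison with all revascularisations and again without CT-prompted ones. Keep symptom-driven procedures in both versions. Counting revascularisation only when it accompanies an acute event would go too far, because it would drop new symptomatic disease that the scan did not prompt.

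The cost is protocol wording and a short addition to the adjudication form. The restricted version will have fewer events and so less precision; the full version is still reported beside it.

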8.7.2. Verification and adjudication of events during follow-up

When an event of interest is reported during study follow-up, the "phase of verification" that consists of obtaining data on: type of event, date, place where it was treated and its corresponding source document (death certificate, epicrisis, complementary study, evolution of clinical history, etc.) where the diagnosis of the event appears with a doctor's signature. The study event adjudication committee will be made up of three medical investigators ([name]). Each of the members will analyze the documentation sent for the case separately and will adjudicate the event. If there is no agreement, it will be awarded by majority.

9. Guarantee and quality control of the data

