8.5. Analysis of cardiac CT

The presence of CAC and its extension will be evaluated using both ordinal variables (number of segments with CAC and number of affected vessels, and qualitatively: absence, mild, moderate, and severe; and the number of coronary segments with calcification) as continuous variables (Agatston units). The presence and extension of calcifications at the level of the aortic valve and the thoracic aorta (Agatston units) will also be evaluated independently. The extent of aortic calcification will be evaluated in sections that include from the bifurcation of the pulmonary artery as the upper limit to the diaphragm as the lower limit.

Quantitative analysis of SCC will be performed using dedicated software (HeartBeat-CS, Philips Healthcare, Best, The Netherlands). Finally, the volume and density of epicardial fat will be calculated by evaluating the volume of tissue with a density between -190 and -30 HU located in the area between the epicardium and the pericardium, the bifurcation of the pulmonary artery as the upper limit, and the diaphragm as lower limit.

Finally, the density of the hepatic parenchyma will be calculated through a region of interest >100 mm² at the level of the right and splenic lobes. From these measurements, the presence of hepatic steatosis will be defined from a quotient of less than 1.

At least 20% of the participants (randomly selected) will have a double reading of the main outcome of the study (presence or extent of CACs). This reading will be carried out by an expert external to the group of researchers of the study and blind to the first reading. In case of disagreement, consensus will be sought between the two experts. The aim of this process is to enhance the internal validity of the study.

The epicardial fat volume analysis will be performed by experts from the University of Palermo (Italy).

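### Section 8.7.2 specifies no masking of the event adjudicators to CT or algorithm results, which could bias judgement-dependent events in exploratory secondary objective 2 (minor)

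*Combined protocol and SAP*

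**What the plan says.** Section 8.7.2 describes verification and adjudication of events reported at the annual telephone call.

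- **Committee.** "The study event adjudication committee will be made up of three medical investigators". They are not described as external to the study team or as independent of recruitment, CT reading or algorithm development.
- **Method.** "Each of the members will analyze the documentation sent for the case separately and will adjudicate the event". On disagreement: "If there is no agreement, it will be awarded by majority".
- **Material.** The source documents include "death certificate, epicrisis, complementary study, evolution of clinical history, etc", and the document must be one "where the diagnosis of the event appears with a doctor's signature".

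The section does not mention masking or removal of study results from the files. The only masking stated in the plan is in Section 8.5, for the second CT reading in at least 20% of participants: "This reading will be carried out by an expert external to the group of researchers of the study and blind to the first reading".

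Section 8.7.1 lists the events. One entry is "Acute ischemic syndrome: Diagnosis of acute myocardial infarction or unstable angina". Heart failure and transient ischaemic attack are also listed. None of the three has diagnostic criteria.

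**The concern.** The adjudicators may know, or read in the file, the measurement that the study is about. If a known high calcium score makes a doubtful episode more likely to be accepted as an event, event status becomes partly a function of calcium. Secondary objective 2 in Section 6 compares transcriptomes between participants with and without a cardiovascular event. The algorithm is trained to recognise coronary calcification, and the preliminary work in Section 5.2 reports genes related to it. Part of any difference found under objective 2 could then come from how events were judged. Events accrue over five years, and a classification made with knowledge of the result is hard to undo afterwards.

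**Working it through.** The plan gives no figure on this point, so the check sets the relevant sections side by side.

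**1. Is masking stated or excluded?** Section 8.7.2 does neither. The coding of participants in Section 9.1 is a confidentiality measure and does not hide a calcium score written in a case file. Section 9.2 provides role-based RedCap access and a procedures manual, still to be written, that covers follow-up. Neither is said to keep results from the adjudicators.

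**2. Can the files carry the result?** Participants attend for a calcium-score CT, some on medical indication (Sections 7.1 and 7.3). Discharge summaries, ancillary tests and clinical histories can plausibly state the score.

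**3. What can be known, and when?** CT is done at baseline, so its result exists for every adjudication. Section 7.1 places sequencing at the end of enrolment. No transcriptome or algorithm output exists before then, and only later adjudications could be made with it available.

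**4. Which events leave room for judgement?**

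| Event | Room for adjudicator judgement |
|---|---|
| Unstable angina, transient ischaemic attack, heart failure | Yes; no criteria in Section 8.7.1 |
| All-cause death | Essentially none |
| Whether a revascularisation was performed | Little; verifiable from records |

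The size of the first group is unclear. Section 8.7 refers to hospitalisations for these conditions, while Section 8.7.1 refers to diagnoses and, for heart failure, to a new diagnosis. The hospitalisation wording narrows the group; the diagnosis wording does not exclude outpatient cases.

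**5. Where would a bias enter?** Only in secondary objective 2. It could enter directly if algorithm output is known, or indirectly through the correlation between calcium and transcriptome if only the CT result is known. The primary objective compares the algorithm with CT and uses no adjudicated event.

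**6. How large?** This cannot be derived. The plan gives no event rate, expected event count, share of doubtful events or agreement rate between adjudicators. The following uses assumptions only, to show what the size would depend on:

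- Let r be the ratio of acceptance rates for doubtful events with and without knowledge of a high score. Assuming 65% to 75% against 60%, r = 0.65/0.60 = 1.08 to 0.75/0.60 = 1.25.
- Let s be the share of doubtful events among accepted events in the reference group, assumed to be 20% to 30%.
- Inflation of the overall event rate ratio = 1 + s × (r − 1). The lowest value is 1 + 0.20 × 0.083 = 1.02; the highest is 1 + 0.30 × 0.25 = 1.08.

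These ratios compare event rates by calcium or algorithm status. Objective 2 compares transcriptomes by event status, and Section 9.4 plans no rate ratio and no event analysis. When only the CT result is known, the effect on objective 2 would be weakened further, to the extent that calcium and transcriptome are imperfectly correlated.

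**The case against.** The strongest reply is that the plan already limits discretion. A signed diagnosis must exist before the committee sees a case, three members judge separately, and the majority decides. The procedures manual may add masking. The affected objective is exploratory.

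Much of this stands. The signed diagnosis narrows what the committee can accept, and the analysis at stake is secondary. But separate review and a majority vote reduce individual error; they do not remove a lean shared by three readers who see the same score. A manual not yet written cannot be relied on.

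Three stronger readings are tempting, and the documents do not support them.

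- **A reader might infer that the adjudicators are unmasked.** The plan is silent. It also does not show whether the members recruit, read CT or work on the algorithm.
- **A reader might take the Section 8.5 masking as a standard that Section 8.7.2 fails to meet.** That reader is blind to the first CT reading, which is a check on reader agreement. It is not masking to the test under study.
- **A reader might infer that masking would remove the whole bias.** Treating doctors may know the score when they diagnose or revascularise, and masking the committee leaves that in place.

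**Conclusion.** The point holds as a gap in the adjudication procedure: masking to CT and algorithm results is not specified and the files are not redacted. Followed as written, the plan allows judgement-dependent events to be classified with knowledge of the calcium score and, for later events, of the algorithm output.

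The consequence is confined to exploratory secondary objective 2. It rests on two premises: that case files or other study roles can reveal the result, and that such knowledge shifts doubtful decisions. Both are plausible; neither is shown in the documents. The size is unknown, and the ratios above rest on assumed rates, so they are not evidence of inflation in this study. Severity: minor. It is still worth settling before adjudication, because masking cannot be restored once events have been judged.

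**What to change.** Add to Section 8.7.2:

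- Existing study staff outside the committee remove the calcium score, other study CT results and transcriptome or algorithm output from each file before it goes to the adjudicators.
- The adjudicators have no RedCap access to these data and stay masked until the follow-up database is locked. The role-based access in Section 9.2 can be used for this.
- A member who already knows a participant's result through another study role declares it. Those events are flagged and examined in a sensitivity analysis of objective 2.

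The committee and its majority rule stay as they are. The cost is some redaction work per event and one further sensitivity analysis. The plan names no role for the redaction, so it has to be assigned. The change addresses the committee's contribution only. Diagnoses and revascularisations prompted by a score known to treating doctors remain and should be stated as a limitation when objective 2 is reported.
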